#### 10.3.1 AEs Experienced Utilizing Investigational Agents and Commercial Agent(s) on the SAME Arm

**NOTE:** *When a commercial agent(s) is (are) used on the same treatment arm as the investigational agent/intervention (also, investigational drug, biologic, cellular product, or other investigational therapy under an IND), the entire combination (arm) is then considered an investigational intervention for reporting.*

#### 10.3.2 Routine Reporting

- Routine AE reporting for Phase 1 and Phase 2 clinical studies using an investigational agent/intervention in combination with a commercial agent is stated in the protocol. See Section 10.6.
- Routine AE reporting for Phase 3 clinical studies using an investigational agent/intervention and a commercial agent in combination must be reported as defined by the general guidelines provided by sponsors, Groups, Cancer Centers, or Principal Investigators. See Section 10.6.

#### 10.3.3 Expedited Reporting

- An AE that occurs on a combination study must be assessed in accordance with the guidelines for investigational agents/interventions in Section 10.4, and where indicated, an expedited report must be submitted.
- An AE that occurs prior to administration of the investigational agent/intervention must be assessed as specified in the protocol. In general, only Grade 4 and 5 AEs that are unexpected with at least possible attribution to the commercial agent require an expedited report. Refer to Section 10.4 for specific AE reporting requirements or exceptions.
- Commercial agent expedited reports must be submitted to the FDA via MedWatch.
- An investigational agent/intervention might exacerbate the expected AEs associated with a commercial agent. Therefore, if an expected AE (for the commercial agent) occurs with a higher degree of severity, expedited reporting is required. The clinical investigator must determine severity.

#### 10.4 Expedited Reporting Requirements for IND/IDE Agents

##### 10.4.1 Phase 1 and Early Phase 2 Studies: Expedited Reporting Requirements for Adverse Events that Occur on Studies under an IND/IDE within 30 Days of the Last Administration of the Investigational Agent/Intervention

###### FDA REPORTING REQUIREMENTS FOR SERIOUS ADVERSE EVENTS (21 CFR Part 312)

**NOTE:** Investigators **MUST** immediately report to the sponsor **ANY** Serious Adverse Events, whether or not they are considered related to the investigational agent(s)/intervention (21 CFR 312.64)

An adverse event is considered serious if it results in **ANY** of the following outcomes:

- 1) Death
- 2) A life-threatening adverse event
- 3) An adverse event that results in inpatient hospitalization or prolongation of existing hospitalization for ≥ 24 hours
- 4) A persistent or significant incapacity or substantial disruption of the ability to conduct normal life functions
- 5) A congenital anomaly/birth defect.
- 6) Important Medical Events (IME) that may not result in death, be life threatening, or require hospitalization may be considered serious when, based upon medical judgment, they may jeopardize the patient or subject and may require medical or surgical intervention to prevent one of the outcomes listed in this definition. (FDA, 21 CFR 312.32; ICH E2A and ICH E6).

**ALL SERIOUS** adverse events that meet the above criteria **MUST** be immediately reported to the sponsor within the timeframes detailed in the table below.

Hospitalization	Grade 1 and Grade 2 Timeframes	Grade 3-5 Timeframes
Resulting in Hospitalization ≥24 hrs	7 Calendar Days	24-Hour 3 Calendar Days
Not resulting in Hospitalization ≥24 hrs	Not required	

###### **Expedited AE reporting timelines are defined as:**

- “24-Hour; 3 Calendar Days” - The AE must initially be reported within 24 hours of learning of the AE, followed by a complete expedited report within 3 calendar days of the initial 24-hour report.
- “7 Calendar Days” - A complete expedited report on the AE must be submitted within 7 calendar days of learning of the AE.

Serious adverse events that occur more than 30 days after the last administration of investigational agent/intervention and have an attribution of possible, probable, or definite require reporting as follows:

**Expedited 24-hour notification followed by complete report within 3 calendar days for:**

- All Grade 3, 4, and Grade 5 AEs

**Expedited 7 calendar day reports for:**

- Grade 2 AEs resulting in hospitalization or prolongation of hospitalization

 For studies using PET or SPECT IND agents, the AE reporting period is limited to 10 radioactive half-lives, rounded UP to the nearest whole day, after the agent/intervention was last administered. Footnote "1" above applies after this reporting period.

Effective Date: May 5, 2011

**NOTE:** Refer to Section 10.3.3 for exceptions to Expedited Reporting

#### 10.4.2 Special situations to Expedited Reporting

##### Exceptions to Expedited Reporting: EXPECTED Serious Adverse Events

An expedited report may not be required for specific Grade 1, 2 and 3 Serious Adverse Events where the AE is EXPECTED. Any protocol specific reporting procedures MUST BE SPECIFIED BELOW and will supersede the standard Expedited Adverse Event Reporting Requirements: Hospitalizations for reasons deemed to be disease related will not be reported.

PET scanning and PET tracer injection are the only procedures unique to this study. The use of hypofractionated radiation therapy is an acceptable form of treatment per National Comprehensive Cancer Network (NCCN) guidelines. All other aspects of radiation therapy and follow-up are part of standard brain cancer treatment. Consequently, only adverse events possibly, probably, or definitely related to F-DOPA-PET administration or radiotherapy will be graded and reported in this protocol. All other toxicities associated with other components of conventional brain cancer treatment (e.g. hematological events resulting from chemotherapy) will not be graded or reported as part of this protocol

System Organ Class (SOC)	Adverse event/ Symptoms	CTCAE Grade at which the event will not be expeditedly reported.
General disorders and administration site conditions	Fatigue	≤Grade 3
Immune system disorders	Allergic Reaction	≤Grade 3
Nervous system disorders	Central nervous system necrosis	≤Grade 3
Nervous system disorders	Vasovagal reaction	≤Grade 3
Injury, poisoning and procedural complications	Bruising	≤Grade 3
Skin and subcutaneous tissue disorders	Rash maculo-papular	≤Grade 3

#### 10.4.3 General reporting instructions

The Mayo IND Coordinator will assist the sponsor-investigator in the processing of expedited adverse events and forwarding of suspected unexpected serious adverse reactions (SUSARs) to the FDA and IRB.

Use Mayo Expedited Event Report form

[REDACTED] for investigational agents or commercial/investigational agents on the same arm.

#### 10.4.4 Reporting of re-occurring SAEs

ALL SERIOUS adverse events that meet the criteria outlined in table 10.4.1 MUST be immediately reported to the sponsor within the timeframes detailed in the corresponding table. This reporting includes, but is not limited to SAEs that re-occur again after resolution.

### 10.5 Other Required Reporting

#### 10.5.1 Persistent or Significant Disabilities/Incapacities

Any AE that results in persistent or significant incapacity or substantial disruption of the ability to conduct normal life functions (formerly referred to as disabilities), congenital abnormalities or birth defects, must be reported immediately if they occur at any time following treatment with an agent under an IND/IDE since they are considered to be a serious AE and must be reported to the sponsor as specified in 21 CFR 312.64(b).

#### 10.5.2 Death

The reporting period for F-DOPA for this study is 1 day.

The reporting period for radiation-related toxicity for this study is 30 days.

Any death occurring within 1 day after F-DOPA agent was last administered or within 30 days of the last radiation dose, regardless of attribution requires expedited reporting within 24-hours.

Any death occurring greater than 1 day after the last F-DOPA agent was administered with an attribution of possible, probable, or definite requires expedited reporting within 24-hours.

Any death occurring greater than 30 days after the last radiation dose was administered with an attribution of possible, probable, or definite requires expedited reporting within 24-hours.

#### Reportable categories of Death

- Death attributable to a CTCAE term.
- Death Neonatal: A disorder characterized by cessation of life during the first 28 days of life.
- Death NOS: A cessation of life that cannot be attributed to a CTCAE term associated with Grade 5.
- Sudden death NOS: A sudden (defined as instant or within one hour of the onset of symptoms) or an unobserved cessation of life that cannot be attributed to a CTCAE term associated with Grade 5.
- Death due to progressive disease should be reported as **Grade 5 “Neoplasms benign, malignant and unspecified (incl cysts and polyps) – Other (Progressive Disease)”** under the system organ class (SOC) of the same name. Evidence that the death was a manifestation of underlying disease (e.g., radiological changes suggesting tumor growth or progression: clinical deterioration associated with a disease process) should be submitted.

### 10.5.3 Secondary Malignancy

- A **secondary malignancy** is a cancer caused by treatment for a previous malignancy (e.g., treatment with investigational agent/intervention, radiation or chemotherapy). A secondary malignancy is not considered a metastasis of the initial neoplasm.
- All secondary malignancies that occur following treatment with an agent under an IND/IDE will be reported. Three options are available to describe the event:
  - Leukemia secondary to oncology chemotherapy (e.g., Acute Myelocytic Leukemia [AML])
  - Myelodysplastic syndrome (MDS)
  - Treatment-related secondary malignancy
- Any malignancy possibly related to cancer treatment (including AML/MDS) should also be reported via the routine reporting mechanisms outlined in each protocol.

### 10.5.4 Second Malignancy

A second malignancy is one unrelated to the treatment of a prior malignancy (and is NOT a metastasis from the initial malignancy). Second malignancies require ONLY routine reporting unless otherwise specified.

## 10.6 Required Routine Reporting

### 10.6.1 Baseline and Adverse Events Evaluations

CTCAE System/Organ/Class (SOC)	Adverse event/Symptoms	Baseline	Post Injection assessment 	Active Monitoring
General disorders and administration site conditions	Fatigue	x		x
Immune system disorders	Allergic reaction		x	
Nervous system disorders	Central nervous system necrosis			x
Nervous system disorders	Vasovagal Reaction		x	
Injury, poisoning and procedural complications	Bruising	x	x	
Skin and subcutaneous tissue disorders	Rash maculo-papular	x	x	
Skin and subcutaneous tissue disorders	Alopecia	x		x
Investigations	Lymphocyte count decreased	x		x
Investigations	Platelet count decreased	x		x
Investigations	Weight loss	x		x
Metabolism	Anorexia	x		x

CTCAE System/Organ/Class (SOC)	Adverse event/Symptoms	Baseline	Post Injection assessment 	Active Monitoring
Nervous system disorders	Encephalopathy	x		x
Nervous system disorders	Headache	x		x
Nervous system disorders	Seizure	x		x
Psychiatric disorders	Confusion	x		x

1. This assessment should occur approximately 15-20 minutes post injection (after scan is completed)

#### 10.6.2 Additional instructions

Submit via appropriate MCCC Case Report Forms (i.e., paper or electronic, as applicable) the following AEs experienced by a patient and not specified in Section 10.6.

10.6.2.1 Grade 2 AEs deemed *possibly, probably, or definitely* related to the study treatment or procedure.

10.6.2.2 Grade 3 and 4 AEs regardless of attribution to the study treatment or procedure.

10.6.2.3 Grade 5 AEs (Deaths) (See Section 10.5.2)

#### 10.6.3 Late Occurring Adverse Events:

Refer to the instructions below and in the Forms Packet (or electronic data entry screens, as applicable) regarding the submission of late occurring AEs following completion of the Active Monitoring Phase (i.e., compliance with Test Schedule – see Section 4.0).

Toxicity will be monitored continuously as each patient is accrued and follow-up data are accumulated. Acute radiation therapy and chemotherapy toxicities will be graded using Common Terminology Criteria for Adverse Events (CTCAE) v4.0 (available at <http://ctep.cancer.gov>). Late toxicities will be reported using the RTOG/EORTC late toxicity criteria.

## 11.0 Treatment Evaluation/Measurement of Effect

### 11.1 Measurement of Effect

Tumor response will be assessed, using contrast and non-contrast brain magnetic resonance imaging (MRI) with assessment based on the RANO criteria, until progression of disease (up to 5 years).

### 11.2 Definitions

Response and progression will be evaluated in this study using the international criteria proposed by the Response Assessment in Neuro-Oncology (RANO) Working Group. Note: Lesions are either measurable or non-measurable using the criteria provided below. The term “evaluable” in reference to measurability will not be used because it does not provide additional meaning or accuracy.

#### 11.2.1 Measurable Disease

Measurable disease is defined as bi-dimensionally contrast-enhancing lesions with clearly-defined margins by MRI, with two perpendicular diameters of at least 10 mm, visible on 2 or more axial slices which are preferably at most 5 mm apart with 0 mm skip. In the event the MRI is performed with thicker slices, the size of a measurable lesion at baseline should be two times the slice thickness. In the event there are inter-slice gaps, this also needs to be considered in determining the size of measurable lesions at baseline.

Measurement of tumor around a cyst or surgical cavity is problematic. In general, such lesions should be considered non-measurable unless there is a nodular component measuring at least 10 mm in diameter. The cystic or surgical cavity should not be measured in determining response. All tumor measurements must be recorded in millimeters (or decimal fractions of centimeters).

#### 11.2.2 Non-measurable Disease

This is defined as either uni-dimensionally measurable lesions, masses with margins not clearly defined, or lesions with maximal perpendicular diameters <10 mm.

#### 11.2.3 Target Lesions

All measurable lesions up to a maximum of five lesions should be identified as target lesions and recorded and measured (sum of the products of the perpendicular diameters) at baseline. Target lesions should be selected on the basis of their size (lesions with the longest diameters) and their suitability for accurate repeated measurements by imaging techniques. Occasionally, the largest lesions may not be suitable for reproducible measurements and the next largest lesions which can be measured reproducibly should be selected.

#### 11.2.4 Non-target Lesions

For patients with recurrent disease who have multiple lesions of which only one or two are increasing in size, the enlarging lesions should be considered the target lesions for evaluation of response. The other lesions will be considered non-target lesions and should also be recorded. Rarely, unequivocal progression of a non-target lesion requiring discontinuation of therapy, or development of a new contrast-enhancing lesion may occur even in the setting of stable disease (SD) or partial response (PR) in the target lesions. These changes would qualify as progression. Non-target lesions also include measurable lesions that exceed the maximum number of 5. Measurements of these lesions are not required but the presence or absence of each should be noted throughout follow-up.

### 11.4 Response Criteria

#### 11.4.1 Evaluation of Target Lesions

11.4.1.1 Complete Response (CR): Requires all of the following:

- Complete disappearance of all enhancing measurable and non-measurable disease sustained for at least 4 weeks
- No new lesions
- Stable or improved non-enhancing (T2-FLAIR) lesions
- Patients must be off corticosteroids
- Stable or improved clinically

Patients with non-measurable disease cannot have a complete response. The best response possible is stable disease.

11.4.1.2 Partial Response (PR): Requires all of the following:

- $\geq 50\%$  decrease compared to baseline in the sum of products of perpendicular diameters of all measurable enhancing lesions sustained for at least 4 weeks
- No progression of non-measurable disease
- No new lesions
- Stable or improved non-enhancing (T2-FLAIR) lesions on same or lower dose of corticosteroids compared to baseline scan
- The corticosteroid dose at the time of the scan evaluation should be no greater than the dose at time of the baseline scan
- Stable or improved clinically

Patients with non-measurable disease cannot have a partial response. The best response possible is stable disease.

11.4.1.3 Stable Disease (SD): Requires all of the following:

- Does not qualify for complete response, partial response, or progression
- Minimum 4 weeks duration
- Stable non-enhancing (T2-FLAIR) lesions on same or lower dose of corticosteroids compared to baseline scan. In the event that the corticosteroid dose has been increased, the last scan considered to show stable disease will be the scan obtained when the corticosteroid dose was equivalent to the baseline dose
- Stable clinically

11.4.1.4 Progression: Defined by any of the following:

- $\geq 25\%$  increase in the sum of products of perpendicular diameters of enhancing lesions compared to the smallest tumor measurement obtained either at baseline (if no decrease) or best response, on stable or increasing doses of corticosteroids
- Significant increase in T2-FLAIR non-enhancing lesion on stable or increasing doses of corticosteroids compared to baseline scan or best response following initiation of therapy, not due to co-morbid events (e.g. radiation therapy, demyelination, ischemic injury, infection, seizures, post-operative changes, or other treatment effects)
- Any new lesion
- Clear clinical deterioration not attributable to other causes apart from the tumor (e.g. seizures, medication side effects, complications of therapy, cerebrovascular events, infection, etc.) or changes in corticosteroid dose. The definition of clinical deterioration is left to the discretion of the investigator but it is recommended that a decrease in 20% of KPS or from any baseline to 50% or less be considered, unless attributable to co-morbid events.
- Failure to return for evaluation due to death or deteriorating condition
- Clear progression of non-measurable disease

11.4.1.5 Pseudoprogression (PsP): All of the following must be true:

- Progression of contrast enhancing lesions and or T2-FLAIR is restricted to the initial radiation therapy volume.
- There are no new enhancing lesions outside of the initial radiation therapy volume.
- Patients are stable or improved clinically.
- PsP may be diagnosed at any time during therapy (beyond the typical 12 week window defined by RANO).

	CR	PR	SD	PD 	Preliminary PD/PsP 
T1-Gd +	None	≥50% decrease	<50% decrease- <25% increase	≥25% increase*	Any increase is restricted to initial RT Volume
T2/FLAIR	Stable or decrease	Stable or decrease	Stable or decrease	Increase*	Any increase is restricted to initial RT Volume
New Lesion	None	None	None	Present*	None
Corticosteroids	None	Stable or decrease	Stable or decrease	NA	Stable or decrease
Clinical Status	Stable or improved	Stable or improved	Stable or improved	Worsened*	Stable or improved
Requirement for Response	All	All	All	Any*	All

CR = complete response; PR = partial response; SD = stable disease; PD = progressive disease, PsP = Pseudoprogression

NA - Increase in corticosteroids alone will not be taken into account in determining progression in the absence of persistent clinical deterioration

1. RANO Progression occurs when any of the criteria with \* are present.
2. Confirmed PD requires all of the following if not all criteria are met then Preliminary PD
  - More than 3 months post RT
  - Radiologic progression by central review [REDACTED] by RANO criteria
  - Clinical progression as determined by treating Oncologist
  - Cannot be considered Pseudoprogression
3. Patients with possible PsP should initially be given the Objective Status of Preliminary Progression. Once PsP or Progression is confirmed, the Objective Status can be changed accordingly.

#### 11.4.1.6 Confirmatory Measurement/Duration of Response

##### 11.4.1.6.1 Confirmation

To be assigned a status of PR or CR, changes in tumor measurements must be confirmed by repeat assessments that should be performed 4 weeks after the criteria for response are first met.

##### 11.4.1.6.2 Duration of Overall Response

The duration of overall response is measured from the time measurement criteria are met for CR or PR (whichever is first recorded) until the first date that recurrent or progressive disease is objectively documented (taking as reference for progressive disease the smallest measurements recorded since the treatment started). The duration of overall CR is measured from the time measurement criteria are first met for CR until the first date that recurrent disease is objectively documented.

##### 11.4.1.6.3 Duration of Stable Disease

Stable disease is measured from the start of the treatment until the criteria for progression are met, taking as reference the smallest measurements recorded since the treatment started.

## 12.0 Descriptive Factors

12.1 Corticosteroid therapy at study entry: Yes (specify dose) vs. no

12.2 IDH1 mutant or wildtype or not available

12.3 ECOG PS (see Appendix I): 0 vs. 1 vs. 2

12.4 Neurologic deficit: Yes vs. no

12.5 History of seizures: Yes vs. no

12.6 Gross total resection vs. Subtotal resection vs. biopsy

12.7 MGMT: Methylated vs. Unmethylated vs. not available

12.8 Family history of brain tumor: Yes vs. no

If yes, check all that apply:

Father/Mother

Brother/Sister

Child

Other (list: )

12.9 Use of alternating electric therapy: yes vs. no

## 13.0 Follow-up Decision at Evaluation of Patient

13.1 A patient is deemed *ineligible* if after registration, it is determined that at the time of registration, the patient did not satisfy each and every eligibility criteria for study entry. The patient will go off study.

- If the patient received MR and F-DOPA-PET for radiotherapy planning, all data up until the point of confirmation of ineligibility must be submitted.
- If the patient never received pre-RT F-DOPA-PET, on-study material must be submitted.

13.2 Those patients who will *not* receive any radiation treatment *or* who will receive radiation treatment elsewhere will move to Event Monitoring phase and be monitored for survival until 5 years after registration.

13.3 Patients who are CR, PR, REGR, or SD will continue to obtain clinically indicated MRI scans for up to 5 years from registration.

13.4 Patients remain on study until all of the following are confirmed / complete (up to 2 years or patient refusal):

- Radiological progression by central review per RANO criteria
- Clinical progression identified by the treating oncologist
- It is more than 3 months since radiation treatments have been completed, to ensure the radiological evidence is tumor progression versus treatment response
- All follow-up study imaging during the patient visit at the time the above three conditions are met is complete

13.5 Patients who develop PD will go to the event-monitoring phase.

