## **8.0 Dosage Modification Based on Adverse Events**

If a patient develops an allergic reaction during injection of F-DOPA, the patient is not to receive any additional tracer and will not undergo PET imaging and will go off study.

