### 16.3.1 Primary Endpoint:

16.3.1.1 Definition: The primary endpoint of this trial is the proportion of alive (overall survival) at 12 months. Survival time is defined as the time from registration to death due to any cause. All patients meeting eligibility criteria who have signed a consent form and who have begun treatment will be evaluable for the endpoint. All eligible patients will be followed until death or a maximum of 5 years.

16.3.1.2 Estimation: The proportion of successes will be estimated by the number of successes divided by the total number of evaluable patients. Confidence intervals for the

true success proportion will be calculated utilizing Exact Binomial methodology. The distribution of survival time will be estimated using the method of Kaplan-Meier (1958).

16.3.1.3 Over Accrual: If more than the target number of patients are accrued, the additional patients will not be used to evaluate the stopping rule or used in any decision making processes; however, they will be included in final point estimates and confidence limits.

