### 16.5.2 Adverse Event Stopping Rules:

As no reactions to F-DOPA have been reported within Mayo Clinic Rochester, toxicity testing reported in the literature revealed no deleterious effects (section 15.0), no reactions are anticipated. As such, at any point in the enrollment process after 10 or more patients have been enrolled, if more than 10% of these patients enrolled are unable to complete PET scanning due to allergic reactions to the tracer, enrollment will be suspended so that details of each episode can be examined and a trial recommendation will be formulated and presented to the MCCC DSMB. There have been no reports in the literature of the occurrence of NSF in patients with normal renal function. Additionally, we will use the contrast agent gadobenate dimeglumine, which has been shown to have a high safety profile (lower incidence of NSF in patients with renal failure/insufficiency) compared with many other available Gd-based contrast agents. Therefore no reactions are anticipated. As such, if at any time a patient develops NSF enrollment will be suspended so that details of the episode can be examined and a trial recommendation will be formulated and presented to the MCCC DSMB.

Using the hypofractionation approach described in Section 7, previous studies have successfully used hypofractionation without significant increases in acute or late adverse effects. However, some studies with more aggressive, higher daily doses of hypofractionation have reported increased toxicity. Nonetheless, both acute (available at <http://ctep.cancer.gov>) and late toxicity will be monitored continuously as each patient is accrued and follow-up data are accumulated. As such, at any point in the enrollment process after 10 or more patients have been enrolled, if more than 10% of these patients enrolled experience any of the following adverse events *considered to be at least possibly related to treatment*, enrollment will be suspended so the details of each episode can be examined and a trial recommendation will be formulated and presented to the DSMB

- Grade 3 or 4 irreversible CNS toxicity
- Grade 4 non-hematologic, non-CNS toxicity
- Any Grade 5 toxicity

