**Test Schedule Material(s)**

CRF	Treatment Phase and Active Monitoring (Compliance with Test Schedule Section 4.0)			Event Monitoring  / Follow-up (Compliance with Test Schedule Section 4.0)
	$\leq$ 4 weeks after each evaluation during RT	$\leq$ 1 week after  F- DOPA- PET scan	End of Treatment	
Radiation Therapy	X		X	
Adverse Event Form (Post Injection of  F- DOPA)		X 		
Radiation Therapy Adverse Event Form (Toxicity)			X 	X 
Off Treatment 	X		X	X
Patient Status Form	X		X	X
Consent Withdrawal 	X	X	X	X

CRF	Treatment Phase and Active Monitoring (Compliance with Test Schedule Section 4.0)			Event Monitoring  / Follow-up (Compliance with Test Schedule Section 4.0)
	$\leq$ 4 weeks after each evaluation during RT	$\leq$ 1 week after $^{18}\text{F}$ - DOPA- PET scan	End of Treatment	
Lost to Follow-up 	X		X	X
Patient Questionnaire Booklet 			X 	X 
Concurrent Steroid and Anticonvulsant Treatment Form			X	X
MMSE			X 	X 
Imaging Form 		X		X

1. Acute toxicity will be assessed during standard of care monitoring by the radiotherapy team during the course of treatment.
2. When applicable.
3. Survey will need to be entered manually if it is not completed electronically
4. Done approximately 15-20 minutes post injection of  $^{18}\text{F}$ -DOPA after scan is completed and if AE observed a second AE assessment is required  $\leq$ 24 hours post injection.
5. Late toxicity will be assessed during standard of care appointments. To be submitted  $\leq$ 2 weeks after each clinically indicated MR scan.
6. Patient will complete a maximum of 6 post-RT QOL evaluations
7. Follow-up is until death or a maximum of 5 years from the time of registration.
8. See Appendix VI.

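### Section 13.1 ends required late-toxicity and survival data for a patient found ineligible after protocol proton radiotherapy, although that patient still counts in the suspension rule and other passages imply follow-up to 5 years

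*Combined protocol and SAP*

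**What the plan says.** **Ineligible patients.** Under Section 13.1, a patient found after registration to be one who "did not satisfy each and every eligibility criteria for study entry. The patient will go off study". The section splits these patients by whether planning imaging was done, not by whether radiotherapy was given. If planning MR and PET were done, "all data up until the point of confirmation of ineligibility must be submitted".

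**Patients not irradiated on study.** Under Section 13.2, patients who get no radiotherapy, or get it elsewhere, "will move to Event Monitoring phase and be monitored for survival until 5 years after registration". This is survival monitoring only.

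**Length of follow-up.** Section 16.3.1.1 says: "All eligible patients will be followed until death or a maximum of 5 years". Note 7 to the test-schedule forms table in Section 18.1 says, with no eligibility condition: "Follow-up is until death or a maximum of 5 years from the time of registration".

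**Analysis sets and rules.** The primary set is defined in Section 16.3.1.1: "All patients meeting eligibility criteria who have signed a consent form and who have begun treatment will be evaluable for the endpoint". The toxicity objective in Section 2.2.2 carries no eligibility limit. The suspension rule in Section 16.5.2 acts, once 10 or more patients are enrolled, "if more than 10% of these patients enrolled experience any of the following adverse events". The listed events include irreversible CNS toxicity of Grade 3 or 4.

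**Expedited reporting.** Sections 10.4.1, 10.5.1 and 10.5.2 keep related late serious events, persistent incapacity and related late deaths reportable, with no exception for ineligible patients. The table in Section 10.4.2 exempts CNS necrosis of Grade 3 or lower.

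**The concern.** A patient can be found ineligible at any time after registration, including after hypofractionated proton treatment guided by PET. From the date of confirmation, Section 13.1 requires no further data. The exposure has happened and its late effects are still to come.

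Two uses of the data suffer. Late toxicity is a secondary objective, and radiation necrosis is central to the rationale: Section 1.1 cites rates of 50% and 20/46 in earlier hypofractionated series, and Section 1.2 offers protons as a possible way to lower them. The suspension rule also counts events per patient enrolled. A treated patient later found ineligible stays in that denominator, while the routine forms through which an event would reach the numerator are no longer due. The rule can then understate the toxicity rate while accrual is still open.

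Section 18.2.1 sets a useful standard for comparison. Even for a subject who revokes authorization, the investigator should seek permission to collect vital status. Section 13.1 makes no such provision for an irradiated, ineligible patient who never withdrew.

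**Working it through.** **1. How many patients could be affected.** Section 16.2.2 gives 39 evaluable patients plus 4 for losses: 39 + 4 = 43, which reproduces the stated maximum accrual. The 4 cover ineligibility, cancellation, major treatment violation and other reasons together. The documents do not say how many would be treated first and found ineligible later. Assumption: k = 0 to 4, that is 0% to 4/43 = 9.3%.

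**2. What still reaches the database for such a patient after confirmation.**

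| Item | Still required? | Source |
|---|---|---|
| Clinical visits and MRI | Continue as clinical care, not as required data | 4.0 notes 1 and 7; 7.1.6; 10.4.2 |
| Related late serious events | Yes, except those exempted in 10.4.2 | 10.4.1, note 1 |
| Persistent incapacity | Yes | 10.5.1 |
| Related late deaths | Yes | 10.5.2 |
| CNS necrosis, Grade 3 or lower | Not expedited; depends on routine forms | 10.4.2, 10.6.1 |
| Routine late-toxicity form | Not under 13.1 | 13.1 against 18.1 notes 5 and 7 |
| Vital status | Not under 13.1 or 16.3.1.1; yes on the plain words of 18.1 note 7 | 13.1, 16.3.1.1, 18.1 |

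The gap that matters is the necrosis row. If irreversible, Grade 3 necrosis is a Section 16.5.2 event, yet it is outside expedited reporting and so relies on the routine data that Section 13.1 ends.

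**3. What one unseen event does to the suspension rule.** The rule needs strictly more than 10% of n enrolled, so the fewest events that trigger it is floor(0.10 × n) + 1:

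- n = 10 to 19: 2 events
- n = 20 to 29: 3 events
- n = 30 to 39: 4 events

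At n = 19, two events give 2/19 = 10.5%, which suspends enrollment. If one of them is in a treated-then-ineligible patient and is not captured, the count is 1/19 = 5.3%, which does not. Taking that patient out of the denominator as well gives 1/18 = 5.6%, still below 10%. Redefining the denominator alone therefore does not repair the rule; the event has to be collected.

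**4. What is unknown about survival.** The smallest passing result is 18/39 = 46.2%. In the extreme case of k = 4 with all four vital statuses unknown, the proportion alive at 12 months among all 43 treated lies between 18/43 = 41.9% and (18 + 4)/43 = 22/43 = 51.2%. Without vital status this range cannot be narrowed. It does not enter the decision rule, which uses eligible patients.

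**The case against.** The strongest reply is that this is a small clarification. Eligibility is checked before registration and a radiation oncologist confirms suitability (Sections 6.1 and 6.3), so the number affected may be zero. Follow-up is largely clinical care, and serious related events and deaths remain reportable. Irreversible Grade 3 necrosis that amounts to persistent incapacity would also fall under Section 10.5.1. All of this stands, and it limits the gap to non-serious or exempted events and to vital status. It does not close the gap: reporting duties act on events that someone identifies and sends in, whereas the routine form asks about them.

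Note 7 in Section 18.1 could be read as already covering these patients. It is attached to the event-monitoring and follow-up column, however, and Section 13.1 sends the patient off study, not into that phase. At best the passages conflict.

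A reader might infer several stronger things that the documents do not support:

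- *Late toxicity and survival are lost in treated patients generally.* Eligible treated patients keep full follow-up.
- *No visit or scan remains.* Both continue as standard care.
- *Follow-up favors untreated over treated patients.* Section 13.1 turns on eligibility and Section 13.2 on where radiotherapy is given; the contrast is a side effect, and Section 13.2 covers survival only.
- *A missed event matters at full accrual (5/43 = 11.6% against 4/43 = 9.3%).* The action is to suspend enrollment, and by then none is left to suspend.
- *Section 8.0 shows the same fault,* because a patient with a tracer reaction "will not undergo PET imaging and will go off study". That reaction comes before protocol radiotherapy and has no bearing on late effects in treated patients.

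**Conclusion.** The point holds for one narrow group: patients irradiated on protocol and later found ineligible. Following Section 13.1 as written ends the requirement for their routine late-toxicity and vital-status data, while they remain in the enrolled denominator of Section 16.5.2. Sections 13.1, 16.3.1.1 and 18.1 do not agree on their follow-up.

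The size is at most 4 of 43 patients (9.3%) if the whole loss allowance fell in this group, and may be zero. Within that range a single uncaptured event can decide whether enrollment is suspended during accrual, as the 2/19 against 1/19 example shows. That example shows sensitivity to one event; it does not show that such an event is likely to be missed.

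A reader might infer that the 12-month survival result is biased. It is not, on the plan's own terms: the primary set is confined to eligible patients who began treatment, and that analysis loses nothing. The change is worth making because it is cheap and because the event most exposed to the gap is the one the regimen is meant to reduce.

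**What to change.** - Amend Section 13.1 so that a patient found ineligible after any protocol radiotherapy moves to event monitoring, with late-toxicity and survival data collected to death or 5 years from registration unless consent is withdrawn. A bare pointer to Section 13.2 is not enough, because that covers survival only.
- State that these patients count in the Section 2.2.2 toxicity analysis and in both numerator and denominator of the Section 16.5.2 rule.
- Keep them out of the primary analysis. Twelve-month survival in all treated patients may be added as an optional descriptive estimate.
- Reconcile Section 13.1, Section 16.3.1.1 and note 7 in Section 18.1 so that all three give the same follow-up for this group.

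The cost is protocol wording and follow-up forms for at most about 4 patients. The toxicity and status forms already sit in the event-monitoring column of the Section 18.1 table, and note 5 there has late toxicity assessed at standard-of-care appointments. No new procedure and no change to the 39 evaluable or 43 accrued is needed.
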